7.1.3 Sensitivity analysis

7.1.3.1 Phase 2

Results of primary analysis will be assessed in sensitivity analyses as detailed below.

- The comparison between treatment and control will be performed by means of a Cox regression model, using age class, gender and clinical severity score at baseline as covariates, to assess the robustness of results on primary endpoint versus the presence of confounding factors. Additional covariates might be included after DRM in case relevant baseline imbalance will be identified between groups, despite randomization. The assumptions of proportionality will be investigated with a time-dependent exploratory variable, which is defined as $\text{treatment} * \{\log[\text{time to event}]\}$. If the p-value from the Wald Chi-squared statistic for this variable is less than 5% there is evidence of a departure from the adjusted model assumptions. In case of non-proportional hazards, a Weibull model will be assumed as parametric form of the distribution of survival times. The treatment group will be included in the model as covariate.
- Time to event for each single component of the primary endpoint will be performed separately in order to adjust for the presence of possible competing risks. The following events:
 - first supplemental oxygen requirement,
 - first mechanical ventilation use,
 - first admission to ICU, and
 - first use of a rescue medication for any reason

will be analyzed according to survival analysis methodology detailed in section 4.1 with the following modifications:

- the common representation of survival curves using the Kaplan-Meier estimator will be replaced by the cumulative incidence function,
- the presence of other competing event(s) is/are treated as censored.
- A modified composite endpoint of phase 2 will be analyzed adding “death” as fifth component. It will be analyzed according to section 7.1.2 to assess the robustness of results on primary endpoint versus the presence of censoring due to fatal events.

Decision to proceed/not proceed to phase 3 will be based only on primary analysis results, despite inconsistencies with sensitivity analyses. Sensitivity results will be interpreted and discussed in the clinical study report and will be used to eventually adjust adaptations for the phase 3.

7.1.3.2 Phase 3

Results of primary analysis will be assessed in sensitivity analyses as detailed below.

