- The comparison between treatment and control will be performed by means of a regression model, using the same method (Cox or Weibull model) and covariates identified during phase 2, to assess the robustness of results on primary endpoint versus the presence of confounding factors.
- Time to event for each single component of the severe primary endpoint will be performed separately in order to adjust for the presence of possible competing risks. The following events:
 - death,
 - first invasive mechanical ventilation use, and
 - first admission to ICU

will be analyzed according to survival analysis methodology detailed in section 4.1 with the following modifications:

- the common representation of survival curves using the Kaplan-Meier estimator will be replaced by the cumulative incidence function,
- the presence of other competing event(s) is/are treated as censored.
- The comparison between treatment and control will be performed in the PP population instead of FAS as described in section 7.1.2, to assess the robustness of trial results versus the adherence to protocol.

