7.2.2 Comparison between treatments

Along with the above summary statistics, comparisons between treatments will be performed as detailed in the next sub-sections. Parametric test (i.e. two-sample t-test for continuous variables, Chi-square test for categorical) will be adopted as first choice. In case the required assumptions are not met, the corresponding non-parametric counterpart will be used (i.e. the two-sample Mann–Whitney U test for continuous variables, and the Fisher’s Exact test for the categorical). Normality of continuous data is assessed by Kolmogorov-Smirnov test.

Comparison will be performed at each available time point, where applicable. Any exception will be declared.

7.2.2.1 *Composite endpoint of phase 2 using Oxygen Delivery System Classification*

The composite endpoints will be summarized along with their single component by a binomial response rate at each time point (only the first event will be considered). The Clopper-Pearson method will be used to estimate the two-sided 95% CIs.

Time to composite endpoint(s) will be performed using the KM methodology and the one-sided log-rank test will be used to test for differences between treatment groups.

7.2.2.2 *Changes in clinical severity score*

Number and proportion along with the 95% confidence interval (Clopper-Pearson’s formula) of subjects with a clinical severity score improvement of at least two points compared to randomization or live discharge from the hospital will be calculated and compared.

7.2.2.3 *Dyspnea severity (Liker scale and VAS scale)*

The comparison of the Liker scale between the two study treatment arms will be performed by means of Wilcoxon signed-rank test, given its ordinal nature.

Number and proportion along with the 95% confidence interval (Clopper-Pearson’s formula) of subjects with

any improvement (improved vs not-improved) will be calculated and compared.

VAS scale comparison between treatments will be performed according to its continuous nature.

7.2.2.4 *Changes in body temperature*

Comparison between treatments in change from baseline of the body temperature will be performed according to the continuous nature of the variable.

7.2.2.5 *Incidence of supplemental oxygen treatment*

Number and proportion along with the 95% confidence interval (Clopper-Pearson's formula) of subjects who worsened according to PaO₂/FiO₂ and to Oxygen Delivery System Classification based on oxygen support will be calculated and compared.

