At each time point the number and proportion of patients within each class (Severe, Moderate, or Mild for PaO₂/FiO₂; Invasive, High Flow, or Low Flow for the type of support) will be provided.

Finally, summary of cumulative quantity (L) and cumulative duration (hours) of oxygen treatment will be performed at 7 days and subsequent time points considering the variable as continuous.

7.2.2.6 *Incidence and duration of mechanical ventilation use*

Number and proportion along with the 95% confidence interval (Clopper-Pearson's formula) of subjects requiring mechanical ventilation will be calculated and compared.

Comparison between treatments in cumulative duration (hours) of mechanical ventilation will be performed at 7 days and subsequent time points considering the variable as continuous. Analysis will be performed overall and stratified by Invasive/Non-invasive mechanical ventilation.

7.2.2.7 *Incidence of ICU admission need*

Number and proportion along with the 95% confidence interval (Clopper-Pearson's formula) of subjects requiring ICU admission will be calculated and compared.

Comparison between treatments in duration (days) of ICU stay will be performed considering the variable as continuous.

7.2.2.8 *Change from baseline in lung damage extension and lung exudation degree (assessed by Chest CT or Rx)*

The comparison of the clinical evaluation of lung damage extension and lung exudation between the two study treatment arms will be performed by means of Wilcoxon signed-rank test.

7.2.2.9 *Respiratory parameters*

Change from baseline of FiO₂, Respiration rate, PaO₂, SpO₂ and PaO₂/FiO₂ will be compared between treatments considering the continuous nature of these variables.

7.2.2.10 *CRP and Hs-CRP*

CRP (mg/L) and Hs-CRP (mg/L) will be compared between treatments considering their continuous nature.

7.3 **Analysis of exploratory efficacy endpoints**

Explorative endpoints (section 3.5.3) will be analyzed at each available time points by means of descriptive statistics. Specifically, analyses will be provided for baseline visit, each post-baseline visit, and the change from baseline measurements to each visit. Comparison between treatments will be performed by means of two-sample t-test or, if assumptions of normality is not confirmed (by Kolmogorov-Smirnov test), two-sample Mann-Whitney U test.

In case of different units of measure considered for the same laboratory parameter, all values will be converted

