Time to supplemental oxygen requirement (days)	Time to supplemental oxygen requirement (days) = First Administration start date - Date of randomization
Time to mechanical invasive ventilation use (days)	Time to (invasive) mechanical ventilation use (days) = First (invasive) Mechanical Ventilation start date - Date of randomization
Time to admission to ICU (days)	Time to admission to ICU (days) = Admission date - Date of randomization
Time to rescue medication (days)	Time to rescue medication (days) = First rescue treatment start date - Date of randomization
Overall survival (days)	Overall survival (days) = Date of death - Date of randomization
Subject with improvement based on Likert scale	Improvement = any of these answers: 
 • 1 = minimally better, • 2 = moderately better, and • 3 = markedly better
Cumulative quantity (L) of oxygen treatment	Cumulative quantity of oxygen treatment (L) = Sum of all Quantity (L) in CONCOMITANT OXYGEN TREATMENT form, from randomization to time point of interest. It is defined as supplemental oxygen requirement any increased used of oxygen compared to baseline.
Cumulative duration (hours) of oxygen treatment	Cumulative duration of oxygen treatment (hours) = Sum of duration of oxygen administration (hours) in CONCOMITANT OXYGEN TREATMENT form, from randomization to time point of interest. Duration of oxygen administration (hours) = Administration end date/time - Administration start date/time / 60
Cumulative duration (hours) of mechanical ventilation	Cumulative duration of mechanical ventilation (hours) = Sum of duration of mechanical ventilation (hours) in MECHANICAL VENTILATION form, from randomization to time point of interest. Duration of mechanical ventilation (hours) = End date/time - Start date/time / 60
Duration (days) of ICU stay	Duration of ICU stay (days) = Discharge date - Admission date
Change from baseline	For changes from baseline the baseline value will constitute the minuend and the later value the subtrahend.
Conversion of Time Intervals	If a time interval was calculated in minutes, hours or days and needs to be converted into months or years the following conversion factors will be used: 
 • 1 hour = 60 minutes • 1 day = 24 hours • 1 week = 7 days • 1 month = 30.4375 days • 1 year = 365.25 days

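### The SAP names a paired test to compare two independent arms, and its fallback for non-proportional hazards is a model that itself assumes proportional hazards

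*SAP*

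**What the plan says.** **Ordinal and imaging endpoints.** SAP 7.2.2.3 says of the dyspnea score: "The comparison of the Liker scale between the two study treatment arms will be performed by means of Wilcoxon signed-rank test". The reason given is that the scale is ordinal. SAP 7.2.2.8 uses the same test for imaging: "lung exudation between the two study treatment arms will be performed by means of Wilcoxon signed-rank test". The opening of SAP 7.2.2 gives as its general non-parametric alternative "the two-sample Mann–Whitney U test for continuous variables", and SAP 7.3 names that two-sample test for the exploratory endpoints. SAP 3.3 randomizes 2:1, stratified by site, without matching patients. The Protocol Summary puts 32 of the 48 Phase 2 patients on reparixin.

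**Adjusted sensitivity model.** SAP 7.1.3.1 fits a Cox model with age class, gender and baseline clinical severity score, and checks proportionality with a 5% Wald test of treatment × log(time). If the check fails: "In case of non-proportional hazards, a Weibull model will be assumed as parametric form of the distribution of survival times". It then adds: "The treatment group will be included in the model as covariate". No arm-specific shape is mentioned. SAP 7.1.3.2 fits the Phase 3 model "using the same method (Cox or Weibull model) and covariates identified during phase 2".

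**Two smaller statements.** For the single components, SAP 7.1.3 replaces the Kaplan-Meier curve with the cumulative incidence function and adds that "the presence of other competing event(s) is/are treated as censored". SAP Table 7 says: "For changes from baseline the baseline value will constitute the minuend and the later value the subtrahend".

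**The concern.** A signed-rank test works on within-pair differences, or on one sample against a fixed value. Neither describes two independent arms. A programmer who follows the text either gets an error, because there are no pairs, or runs the test within each arm. The second route is easy to take. The dyspnea score is already a change score, with 0 meaning no change (Protocol 7.2), and the imaging endpoints are changes from baseline. The output would then say whether each arm changed, not whether the arms differ. Either way the test actually used would be settled after data exist, in an open-label trial.

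The Weibull fallback has a different fault. It is invoked only when the data have rejected a constant hazard ratio, and it then imposes one. The model meant to show robustness to confounding would summarise a time-varying effect with a single number. SAP 7.1.3.1 also allows sensitivity results to inform the Phase 3 adaptations, so the number has some use beyond the report.

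**Working it through.** No figure in the plan is disputed, so there is none to reproduce. Every distribution below is an assumption.

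**1. Signed-rank test.** Inputs: 32 reparixin and 48 − 32 = 16 control patients. A two-sample call to the signed-rank test with 32 and 16 unmatched scores returns an error. To size the by-arm reading, both arms were given the same distribution on −3 to 3, with probabilities .02, .05, .10, .25, .31, .18, .09. The mean is −0.06 − 0.10 − 0.10 + 0 + 0.31 + 0.36 + 0.27 = 0.68. With 6,000 simulated trials and two-sided 5% tests:

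| Result, with no difference between arms | Share of trials |
|---|---|
| Signed-rank significant in reparixin | 76.0% |
| Signed-rank significant in control | 44.2% |
| Significant in reparixin only | 42.6% |
| Rank-sum test between arms significant | 5.0% |

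Because the arms are independent, the third row should be close to 0.760 × (1 − 0.442) = 0.424, and it is. The asymmetry arises because 32 patients give more power against zero than 16 do. At a common mean of 0.46 the reparixin-only share is 30.8%, and at 1.17 it is 13.9%; the rank-sum test rejects in 4.9% and 4.5%.

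**2. Weibull model.** With common shape k, and treatment shifting log time by b, the hazard ratio is HR(t) = exp(−k·b), which does not contain t. For b = 0.7 it is 0.657 (k = 0.6), 0.497 (k = 1) and 0.350 (k = 1.5) at every day from 1 to 21.

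As a scenario, take an exponential control arm with λ = ln 2 / median, using the 2 to 4 day range of SAP Table 2. Let the reparixin hazard ratio be 1 to day 2 and 0.3 afterwards, with 2:1 allocation and censoring at day 21. The Weibull was fitted by maximum likelihood to 600,000 simulated patients. The restricted means come from integration:

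- control: (1 − e^(−21λ)) / λ
- reparixin: (1 − e^(−2λ)) / λ + e^(−2λ) · (1 − e^(−0.3λ·19)) / (0.3λ)

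For a 2-day median, λ = 0.3466. Control is 2.88 days; reparixin is 1.44 + 4.14 = 5.58 days.

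| Control median | Fitted HR (shape) | Control mean | Reparixin mean | Difference |
|---|---|---|---|---|
| 2 days | 0.575 (0.79) | 2.88 | 5.58 | 2.7 days |
| 3 days | 0.508 (0.79) | 4.29 | 8.25 | 4.0 days |
| 4 days | 0.469 (0.80) | 5.62 | 10.23 | 4.6 days |

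The fitted ratio describes neither period: it is 1 early and 0.3 late. A harsher case uses a control arm with shape 0.7 and scale 5 days, and a reparixin arm with shape 1.6 and scale 8 days. The true hazard ratio runs from 0.25 on day 1 through 1.46 on day 7 to 3.92 on day 21, and the model returns 0.82 throughout.

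**3. Competing events (minor).** If the censoring statement were applied to the curve, the result would be 1 − KM. For a component with share s of a constant hazard, and a 2-day median, 21λ = 7.278. Then 1 − KM = 1 − exp(−7.278·s), and the cumulative incidence is s·(1 − e^(−7.278)). For s = 10%, 25% and 50%, 1 − KM reads 52%, 84% and 97% at day 21, against a true 10%, 25% and 50%.

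**4. Sign of change (minor).** Baseline minus later value makes a rise in PaO2/FiO2 print as negative. Two-sided p-values do not change.

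**The case against.** The signed-rank wording is probably a slip for rank-sum. Both sentences concern a comparison between arms, and no by-arm test against zero appears in the SAP. The 43% therefore measures a possible misuse, not a planned analysis, and a programmer who met the error might simply substitute the rank-sum test. This stands as a limit on the figure. It does not rescue the text: the name occurs twice, and SAP 7.2.2 defers to its sub-sections, so the specific instruction governs. It is also fair that SAP 7.2.2 names Mann-Whitney for continuous variables only. The mismatch is therefore less a strict contradiction than a sign of what was probably meant.

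The Weibull model applies only if the check fires. In the scenario above, with 32 v 16 patients, an unadjusted Cox check fires in about 32%, 33% and 30% of trials for control medians of 2, 3 and 4 days (600 trials each). Otherwise the Cox model stays and also gives one ratio. That bounds how often the fault appears but does not make the fallback suitable when it is used. The model could be reported as an accelerated-failure-time model with a time ratio, but with a common shape it remains proportional-hazards. An arm-specific shape would relax this, but the SAP does not provide for one.

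Censoring competing events is normal for a cause-specific log-rank test, and the statement just before it already asks for cumulative incidence. The 52%, 84% and 97% arise only under the unfavourable reading.

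**Conclusion.** Both main points hold. As written, the ordinal dyspnea comparison and the two imaging comparisons cannot test the treatment difference, and the fallback for non-proportional hazards keeps the assumption that the data have just rejected. The sizes rest on the assumed score distributions and the assumed delayed effect; the logical faults do not.

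The reach is limited to secondary and sensitivity analyses. The primary log-rank test, alpha and power are untouched, and SAP 7.1.3.1 bases the decision to proceed on the primary analysis alone. The improved/not-improved comparison of the dyspnea score is also unaffected. Imaging comparisons arise mainly at end of treatment, since other post-baseline imaging is at the investigators' discretion (SAP Table 1). The competing-event wording is an ambiguity and the sign of change is labelling only. The two main points should be corrected, and the minor ones can go with them.

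**What to change.** - **SAP 7.2.2.3 and 7.2.2.8:** name the Wilcoxon rank-sum (Mann-Whitney) test.
- **SAP 7.1.3.1 and 7.1.3.2:** if proportional hazards are rejected, use the difference in restricted mean event-free time to day 21, or a Cox model with a treatment-by-time term. Prespecify which, and keep age class, gender and baseline clinical severity score as covariates.
- **SAP 7.1.3, components:** state that the cumulative incidence curve treats other events as competing (Aalen-Johansen), and that they are censored only for the cause-specific log-rank test.
- **SAP Table 7:** define change as later value minus baseline.

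The cost is SAP wording and minor programming. Sample size, alpha and data collection do not change.

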## 9.4.2.5 Secondary Efficacy Analyses

Each component of the primary composite endpoints will be evaluated separately, and their 95% C.I. will be reported. In addition to descriptive statistics, all secondary endpoints will be analyzed by appropriate parametric tests depending on the nature of the variable and its distribution. Data transformation might be used in order to satisfy the assumption of normality requested by parametric statistical tests. In case such assumptions are not met, non-parametric counterpart tests will be used. Details will be provided in the SAP.

Change from baseline value (for continuous variables) and shift tables versus baseline (for categorical variables) will also be summarized for all post-baseline visits.

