4.8 Handling of missing and incomplete data

The number of subjects with missing data will be presented under the "Missing" category, if present. Missing values will not be included in the denominator count when computing percentages. Similarly, only the non-missing values will be evaluated for computing summary statistics for continuous endpoint. Any exception will be clarified as a note.

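### Ventilation hours and ICU days are compared between arms with no rule for death, so an early death scores like early weaning and the arm with faster death can look better

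*SAP*

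**What the plan says.** SAP 7.2.2.6 plans the following for ventilation: "Comparison between treatments in cumulative duration (hours) of mechanical ventilation will be performed at 7 days and subsequent time points", with the variable treated as continuous. SAP 7.2.2.7 adds: "Comparison between treatments in duration (days) of ICU stay will be performed considering the variable as continuous". The general rule in SAP 7.2.2 sets the test: "Parametric test (i.e. two-sample t-test for continuous variables, Chi-square test for categorical) will be adopted as first choice". The Mann-Whitney test replaces the t-test if its assumptions fail.

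Table 7 in SAP 9.1 derives ventilation hours as the "Sum of duration of mechanical ventilation (hours) in MECHANICAL VENTILATION form, from randomization to time point of interest", and for ICU time it gives "Duration of ICU stay (days) = Discharge date - Admission date". Neither rule mentions death. Neither section says whether a patient who was never ventilated, or never in ICU, counts as zero or is left out. On missing data, SAP 4.8 says that "only the non-missing values will be evaluated for computing summary statistics for continuous endpoint".

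Oxygen is worded differently. SAP 7.2.2.5 says that a "summary of cumulative quantity (L) and cumulative duration (hours) of oxygen treatment will be performed at 7 days and subsequent time points". Only the general text points to a test of oxygen: SAP 7.2.2, and Protocol 9.4.2.5, under which "all secondary endpoints will be analyzed by appropriate parametric tests depending on the nature of the variable and its distribution".

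Death is handled in other places: the phase 3 primary composite, a modified phase 2 composite used as a sensitivity analysis (SAP 7.1.3.1), category 7 of the severity scale, and the safety tables.

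**The concern.** Death ends ventilation and ICU time. A raw duration cannot distinguish a patient who left the ventilator because he recovered from one who left it because he died. In both cases a shorter time reads as the better result.

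What is at stake is how the secondary results are read. The SAP acknowledges the issue for the primary endpoints, where it adds death to the phase 2 composite and invokes competing risks for the components, but not for the durations. It matters most in phase 2. The phase 2 primary composite does not include death, and SAP 4.7 lets phase 2 results inform the choice of phase 3 endpoints and population enrichment.

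**Working it through.** **Inputs.** The documents give no ventilation, weaning or death rates and no target difference for these endpoints, so there is no figure of the plan's own to reproduce. The rates below are assumptions. From the documents come the 21-day follow-up and the 2:1 allocation (SAP 3.2), the 48 and 111 patients, and the two derivations in Table 7.

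**Step 1, direction.** Let *a* be the weaning rate and *b* the death rate on the ventilator, both constant. Time to the first of the two has mean 1/(*a*+*b*). Among patients who are weaned, the mean is also 1/(*a*+*b*). A higher *b* therefore shortens the mean whether deaths end the duration or are dropped. With *a* = 1/12 per day:

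- *b* = 1/24: 8 days, 33% die
- *b* = 1/12: 6 days, 50% die
- *b* = 1/6: 4 days, 67% die

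**Step 2, 21-day illustration.** Assume 40% ventilated in both arms, start uniform over days 0 to 7, *a* = 1/12 in both arms, and *b* = 1/24 (control) or 1/6 (reparixin). Write *r* = *a*+*b*, and *m* for the chance of still being on the ventilator at day 21: *m* = (e^(−14*r*) − e^(−21*r*))/(7*r*). Mean ventilated time is (1−*m*)/*r* and the share of ventilated patients who die is (*b*/*r*)(1−*m*).

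- Control: *r* = 1/8, *m* = (0.1738 − 0.0724)/0.875 = 0.116. Mean 8 × 0.884 = 7.07 days = 170 h. Per randomized patient 0.4 × 170 = 68 h. Deaths 0.4 × (1/3) × 0.884 = 12%.
- Reparixin: *r* = 1/4, *m* = (0.0302 − 0.0052)/1.75 = 0.014. Mean 4 × 0.986 = 3.94 days = 95 h. Per randomized patient 0.4 × 95 = 38 h. Deaths 0.4 × (2/3) × 0.986 = 26%.

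In simulation with deaths dropped, ventilated patients average 182 h (control) and 103 h (reparixin), so that route points the same way.

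**Step 3, free days.** Score 21 minus ventilated days if alive at day 21, and 0 if dead. For a ventilated patient starting on day *s*, the mean is ∫ *a*(21−*x*)e^(−*rx*) d*x* from 0 to 21−*s*, plus *s*·e^(−*r*(21−*s*)), averaged over *s*. This gives 9.44 days (control) and 5.73 (reparixin). Over all patients: 0.6 × 21 + 0.4 × 9.44 = 16.4, against 0.6 × 21 + 0.4 × 5.73 = 14.9. The sign turns.

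**Step 4, range.** With 20 to 60% ventilated and a reparixin death rate of 1/12 to 1/6, the sign turns in every case. The ends, control against reparixin:

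- 20% ventilated, *b* = 1/12: 34 vs 27 h; 18.7 vs 18.4 free days
- 60% ventilated, *b* = 1/6: 102 vs 57 h; 14.1 vs 11.8 free days

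**Step 5, counter-case.** Let the deadlier arm also ventilate more: 30% with *b* = 1/24 on control, 50% with *b* = 1/12 on reparixin. Raw hours are 0.3 × 169.8 = 50.9 and 0.5 × 135.8 = 67.9. Here they point the right way.

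**Step 6, what the tests would do.** Take a deliberately extreme case: 30% ventilated in both arms, survivors ventilated for 240 h, half of the ventilated reparixin patients dead at 48 h, no control deaths. Mean hours are 0.3 × 240 = 72 (control) and 0.3 × (0.5 × 48 + 0.5 × 240) = 43.2 (reparixin). Free days are 0.7 × 21 + 0.3 × 11 = 18.0 and 0.7 × 21 + 0.15 × 11 + 0 = 16.35. Simulated at 32 vs 16 and at 74 vs 37 patients, two-sided 0.05:

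- Mann-Whitney on hours, all patients: falsely favours reparixin in about 5 to 8% of trials.
- Mann-Whitney on hours, ventilated patients only: about 32% at the smaller size and 94% at the larger.
- Rank-sum on free days: detects the harm in about 3 to 6%.

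**The case against.** The strongest objection is that little depends on these variables. Superiority rests on the two primary tests, and progression to phase 3 on the primary analysis alone (SAP 7.1.1 and 7.1.3.1). Deaths are tabulated, and ventilation and ICU incidence are compared beside the durations. All of this stands. A reader might infer that the gap could produce a false primary claim; the documents do not support that.

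A reader might also infer that a drug that kills faster must look better here. Step 5 shows otherwise: the reversal needs similar ventilation or ICU incidence in the two arms.

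A third tempting reading is that ICU deaths are dropped. That depends on whether the CRF records a discharge date at death, which the documents do not say. SAP 4.8 concerns summary statistics and sets no rule for tests.

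A fourth is that oxygen is a planned comparison on the same footing. SAP 7.2.2.5 calls it a summary, and a test follows only from the general rule.

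Finally, the contrast of means overstates what a rank test on all patients would show, and the rank-sum test on free days has little power against the harm in step 6. Both are true. They limit the effect on p-values but do not remove the misleading direction of the reported means. The effect on p-values is large if only ventilated patients are compared, a choice that the SAP leaves open.

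**Conclusion.** The concern holds in this limited form. As written, SAP 7.2.2.6 and 7.2.2.7 with Table 7 give an early death the same credit as early weaning or early ICU discharge. With similar incidence in the two arms, the arm with faster death can look better. On the assumed rates, reparixin shows about 30 fewer ventilation hours per patient (68 − 38) with 14 percentage points more deaths (26 − 12), while free days are 1.5 lower (16.4 − 14.9). The size rests wholly on those assumed rates; the direction rests on similar ventilation incidence.

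The point affects the reading of secondary results and of phase 2 evidence carried forward, not the primary claim. It is worth correcting because the correction is cheap.

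**What to change.** In SAP 7.2.2.6 and 7.2.2.7, make the between-arm comparison ventilator-free days and ICU-free days to day 21 in all FAS patients, tested by Wilcoxon rank-sum. Score death by day 21 as 0, whether or not the patient was ventilated or in ICU. Score a patient alive at day 21 and never ventilated (or never in ICU) as 21. Add both derivations to Table 7.

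Keep raw ventilation hours and ICU days as descriptive summaries, split by survivors and non-survivors, with the number of deaths beside them. If oxygen in 7.2.2.5 is to be tested under the general rule, apply the same approach; if not, say that it is descriptive only.

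The cost is SAP text and programming. Table 7 already uses the death date and the ventilation and ICU start and end dates. There are three downsides:

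- Free days are a less direct unit than hours.
- Ventilation duration is a protocol-named secondary endpoint, so making it descriptive needs an entry in SAP 4.9, which now reports no change. ICU days are not a listed endpoint (SAP 3.5.2 names only incidence).
- Status to day 21 needs a stated assumption for patients discharged alive earlier, for example free of support after discharge. The horizon also needs reconciling. SAP 3.2 assumes 21 days of follow-up. The protocol summary allows up to 21 days of treatment plus a follow-up of up to 7±3 days, so a patient treated for only 7 days could finish by day 17 at the latest (7 + 10).
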